### Chemistry and Hematology, Weight

Week 1, Day 2	2	2-3
Week 1, Day 8	8	4-12
Week n, Day 7*n+1 (n = 2, 3, 4, 5, 6, 7)	7*n+1	Target day -2, Target day +4
Week 8, Day 57	57	55-71
Week n, Day 7*n+1 (n=12, 16, 20, ..., to 104 in increments of 4)	7*n+1	Target day -13 days, Target day + 14 days
Week 108, Day 757	757	744, 764
Week n, Day 7*n+1 (n=110, ..., to 258 in increments of 2)	7*n+1	Target day -6 days, Target day + 7 days
Week 260, Day 1821	1821	1815, SFU -1 if SFU* is available, otherwise >1814

\*study day corresponding to safety follow-up visit assessment

### Pharmacodynamic assessments

Week 1, Day 2	2	2-3
Week 1, Day 4	4	4-6
Week 1, Day 8	8	7-9
Week 1, Day 11	11	10-12
Week 2, Day 15	15	13-19

Week 3, Day 22	22	20, Day 29 - 3
Week 4, Day 29	29	Day 29 -2, Day 29
Week 4, Day 30	30	Day 29 +1
Week 4, Day 32	32	Day 29 + 2, Day 29 +4
Week 5, Day 36	36	Day 29 + 5, 40
Week n, Day 7*n+1 (n = 6,7,8,9,10,11)	7*n+1	Target day -2, Target day +4
Week 12, Day 85	85	83, 92
Week 14, Day 99	99	93, Day 113 -7
Week 16, Day 113	113	Day 113- 6, Day 113
Week 16, Day 114	114	Day 113 +1
Week 16, Day 116	116	Day 113+ 2, Day 113 +4
Week 17, Day 120	120	Day 113 +5, 124
Week 18, Day 127	127	125- 134
Week n, Day 7*n+ 1 (n= 20, 22, ..to 50 in increments of 2 )	7*n+1	Target day -6 days, Target day + 7 days
Week 52, Day 365	365	359-379
Week n, Day 7*n+ 1 (n= 56, 60, 64, ..., to 104 in increments of 4)	7*n+1	Target day - 13 days, Target day + 14 days
Week 108, Day 757	757	744, 764

Week n, Day $7^*n+1$ (n=110, ..., to 258 in increments of 2)	$7^*n+1$	Target day -6 days, Target day + 7 days
Week 260, Day 1821	1821	>1814

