Doses of investigational product must be given within \pm 1 day of the scheduled time point. Subjects will remain at the site for at least 1 hour following the first and second dose of efavaleukin alfa and for 30 minutes following all remaining doses. Once [REDACTED] has been selected, investigational product will be administered within \pm 2 days.

ⁿ Subjects continuing to receive treatment during the extended dosing period will receive efavaleukin alfa treatment at the week 52 visit per their current dosing regimen.

Table 2-3. Phase 1b Schedule of Activities – Extended Dosing Period Subjects Only (Week 53 Through Week 104)

	Visits for weekly dosing	Treatment Period ^a																							PD Visit	SFU/ EOS ^b			
		Visits for weekly and biweekly dosing																											
Study Week	53,55,57,59,61,63,65,67,69,71,73,75,77,79,81,83,85,87,89,91,93,95,97,99,101,103	54	56	58	60	62	64	66	68	70	72	74	76 ^c	78	80	82	84	86	88	90	92	94	96	98	100	102	104/ EOET ^d	Any-time	
Study Day	372,386,400,414,428,442,456,470,484,498,512,526,540,554,568,582,596,610,624,638,652,666,680,694,708,722	379	393	407	421	435	449	463	477	491	505	519	533	547	561	575	589	603	617	631	645	659	673	687	701	715	729		
GENERAL ASSESSMENTS																													
Physical Examination																												X	
Vital Signs	X	X	X	X	X	X	X	X	X	X	X	X	X	X	X	X	X	X	X	X	X	X	X	X	X	X	X		
Weight													X														X		
ECG ^e													X														X	X	X
Concomitant Medication	X	X	X	X	X	X	X	X	X	X	X	X	X	X	X	X	X	X	X	X	X	X	X	X	X	X	X		
Corticosteroid use ^f	X	X	X	X	X	X	X	X	X	X	X	X	X	X	X	X	X	X	X	X	X	X	X	X	X	X	X		
Adverse Events	X	X	X	X	X	X	X	X	X	X	X	X	X	X	X	X	X	X	X	X	X	X	X	X	X	X	X		
Serious Adverse Events	X	X	X	X	X	X	X	X	X	X	X	X	X	X	X	X	X	X	X	X	X	X	X	X	X	X	X		
Disease-Related Events	X	X	X	X	X	X	X	X	X	X	X	X	X	X	X	X	X	X	X	X	X	X	X	X	X	X	X		
NIH cGVHD Response Assessment (NIH Form A) ^g													X														X	X	
Pulmonary Function Test ^h													X														X	X	

Page 1 of 2

Footnotes defined on last page

Table 2-3. Phase 1b Schedule of Activities – Extended Dosing Period Subjects Only (Week 53 Through Week 104)

	Visits for weekly dosing	Treatment Period ^a																									PD Visit	SFU/ EOS ^b	
		Visits for weekly and biweekly dosing																											
Study Week	53,55,57,59,61, 63,65,67,69,71, 73,75,77,79,81, 83,85,87,89,91, 93,95,97,99,101, 103	54	56	58	60	62	64	66	68	70	72	74	76 ^c	78	80	82	84	86	88	90	92	94	96	98	100	102	104/ EOET ^d	Any-time	

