	372,386,400,414, 428,442,456,470, 484,498,512,526, 540,554,568,582, 596,610,624,638, 652,666,680,694, 708,722	379	393	407	421	435	449	463	477	491	505	519	533	547	561	575	589	603	617	631	645	659	673	687	701	715	729		
CLINICAL OUTCOME ASSESSMENTS																													
LABORATORY ASSESSMENTS																													
Clinical Chemistry and Hematology					X		X		X		X		X		X		X		X		X		X		X		X		X
Pregnancy Test ^f				X		X		X		X		X		X		X		X		X		X		X		X		X	
PHARMACOKINETIC AND ANTIBODY ASSESSMENTS																													
OTHER																													
Lymphocyte Subsets ^l						X			X			X			X			X			X			X			X		
Biomarker Development Sample ^l						X			X			X			X			X			X			X			X		
DOSE																													
Weekly Efavaleukin Alfa Administration ^m	X	X	X	X	X	X	X	X	X	X	X	X	X	X	X	X	X	X	X	X	X	X	X	X	X	X	X	X ⁿ	
Biweekly Efavaleukin Alfa Administration ^m		X	X	X	X	X	X	X	X	X	X	X	X	X	X	X	X	X	X	X	X	X	X	X	X	X	X	X ⁿ	

CRF = case report form; cGVHD = chronic graft versus host disease; ECG = electrocardiogram; EOS = end of study for individual subject; EOET = end of extended treatment; GVHD = graft versus host disease; NIH = National Institutes of Health; PD = progressive disease; PFT = pulmonary function test; PK = pharmacokinetics; Q2W = twice weekly; QW = every week; [REDACTED]; SFU = safety follow-up

^a Subjects who withdraw early from treatment will complete the EOET visit and Safety follow-up visit within a window of \pm 7 days of the next regularly scheduled visit after the last dose of efavaleukin alfa, consisting of all assessments included in the week 104 visit.

^b Safety follow-up visit will be done 6 weeks (\pm 3 days) after the last dose of efavaleukin alfa. Women of childbearing potential will be required to complete a pregnancy test at this visit.

^c Re-assessment of subject's response to efavaleukin alfa treatment will be conducted at week 76 and a decision may be made by the Sponsor, following discussion and agreement between the principal investigator and medical monitor, to allow subjects who wish to, to continue treatment through week 102 (Q2W dose) or week 103 (QW dose).

^d Subjects in the extended dosing period who discontinue treatment prior to week 258 (Q2W dosing) or week 259 (QW dosing) for any reason will complete an EOET visit and 6-weeks of safety follow-up after the last dose of efavaleukin alfa.

^e A single ECG will be collected prior to blood draws or other invasive procedures. See Section 9.2.3.3.

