9.1.2 Treatment Period

Visits will occur per the Schedule of Activities (see [Table 2-1](#), [Table 2-2](#), [Table 2-3](#), [Table 2-4](#), [Table 2-5](#), [Table 2-6](#), [Table 2-7](#), and [Table 2-8](#)). In the phase 1b part of the study, visits may be completed within a visit window of \pm 1 day through the week 4 visit. After the week 4 visit, the visit window may increase to \pm 3 days from the scheduled visit date for those phase 1b subjects on Q2W dosing and \pm 2 days from the scheduled dose date for those subjects on QW dosing.

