9.2.5 Pharmacokinetic Assessments

9.2.6 Pharmacodynamic Assessments

Lymphocyte Subsets: Blood samples will be collected for all subjects at the time points indicated in the Schedule of Activities. These samples will be used to evaluate Treg, Tcon, and NK cells. Sampling time points for lymphocyte subsets may be modified based on emerging data.

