## Appendix G. Analytical Windows

The last visit with non-missing assessment prior to first dose will be defined as a baseline visit (unless specified otherwise) and the analysis visit name will be “Baseline”. For any visit up to Day 1 pre-dose which is not a baseline visit, the analysis visit will be ‘Pre-Analysis’. For Day 1 post-dose visits, and safety follow-up visit, the analysis visit will be same as the scheduled visit. For any unscheduled visit post safety follow-up visit, the analysis visit will be considered as safety follow-up visit. For post-dose assessments on Day 29 (the day corresponding to Week 4 dosing) and Day 113 (the day corresponding to week 16 dosing), the analysis visit will be same as the scheduled visit. Remaining visits (scheduled visit, unscheduled visit, progressive disease visit, or end of treatment visit) after Day 1 for any assessment will be mapped to the analysis visit based on visit windows defined in the tables below for that assessment. Only visits applicable for that assessment and phase of the study as per the Schedule of Activities tables in the study protocol will be considered for analysis.

Data collected through central lab and local lab will both be mapped into analysis visit windows. The local lab data can only be used in analysis when there is no central lab data available in the analysis visit window.

If more than one visit with non-missing data falls within an analysis visit window, the visit closest to the target day will be considered for analysis. If two visits are equidistant from the target day, the latest visit (or time if on the same day) will be considered. If more than one evaluation has same date and time (for chemistry, hematology or pharmacodynamics results), the value with the smallest accession number will be considered.

Analysis visit windows for selected assessments are included in tables below. For remaining assessments, no visit window will be applied. Day 29 and Day 113 used in Study day window calculation in the tables below is the respective study day when Week 4 dose and Week 16 dose was received. If that dose is missing, then 29 and 113 is used for respective calculation.

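### For weeks 53 to 104 the SAP's 4-weekly pharmacodynamic windows do not fit the 6-weekly lymphocyte-subset schedule, and 4 of 8 scheduled samples get the wrong visit label

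*SAP*

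**What the plan says.** **SAP.** The pharmacodynamic table in Appendix G lists, after week 52 (days 359 to 379), analysis visits at "n= 56, 60, 64, ..., to 104 in increments of 4" with the window "Target day - 13 days, Target day + 14 days". That makes 13 windows of 28 days. They are followed by week 108 (days 744 to 764) and then by 2-weekly windows, "n=110, ..., to 258 in increments of 2". The introduction to Appendix G sends scheduled, unscheduled, progressive-disease and end-of-treatment visits after day 1 through these windows, so the nominal visit does not fix the label. It also limits the analysis: "Only visits applicable for that assessment and phase of the study as per the Schedule of Activities tables".

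**Protocol.** Section 9.2.6 makes lymphocyte subsets (Treg, Tcon and NK cells) the pharmacodynamic assessment: "Lymphocyte Subsets: Blood samples will be collected for all subjects at the time points indicated in the Schedule of Activities". In Table 2-3 (weeks 53 to 104), the row "Lymphocyte Subsets ^l" has 8 marks, each three 2-week columns apart, ending at week 104/EOET. They fall at weeks 62, 68, 74, 80, 86, 92, 98 and 104. The biomarker row is identical, while the chemistry row of the same table is 4-weekly.

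**The concern.** The two lists share only weeks 68, 80, 92 and 104. The other four sampling weeks lie midway between two SAP target weeks, where a one-day difference decides the label. Late visits are permitted: Protocol Section 9.1.2 allows 3 days either side for Q2W subjects and 2 days for QW subjects after week 4.

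If the extension is summarised by analysis visit, one sampling occasion can be reported as two visits, with subjects divided by whether they came late. Planned cohorts have 3 to 6 DLT-evaluable subjects, and only responders may continue past week 52, so the number per label is already small. Part of the apparent Treg time course could then reflect visit timing. The pharmacodynamic row has the same step and width as the chemistry and antibody rows for these weeks, which suggests that it was carried over from them.

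**Working it through.** **1. Target days.** Appendix G uses target day = 7n + 1 for week n. Table 2-3 prints the study days for weeks 54 to 64 as "379 393 407 421 435 449". The formula gives 7 × 54 + 1 = 379, 7 × 62 + 1 = 435 and 7 × 64 + 1 = 449, and it reproduces all 26 printed days up to week 104 (729). Protocol and SAP therefore share one day scale.

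**2. Where each window ends.** The last day of the week-n window is (7n + 1) + 14 = 7(n + 2) + 1, which is the target day of week n + 2. A sample scheduled two weeks after a SAP target week therefore always falls on a window boundary.

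**3. Mapping the eight scheduled samples.**

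| Scheduled week | Day | SAP window containing it | Label if on time or early | Label if 1 to 3 days late |
|---|---|---|---|---|
| 62 | 435 | week 60: 408-435 | 60 | 64 (436-463) |
| 68 | 477 | week 68: 464-491 | 68 | 68 |
| 74 | 519 | week 72: 492-519 | 72 | 76 (520-547) |
| 80 | 561 | week 80: 548-575 | 80 | 80 |
| 86 | 603 | week 84: 576-603 | 84 | 88 (604-631) |
| 92 | 645 | week 92: 632-659 | 92 | 92 |
| 98 | 687 | week 96: 660-687 | 96 | 100 (688-715) |
| 104 | 729 | week 104: 716-743 | 104 | 104 |

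Weeks 62, 74, 86 and 98 never receive their own label. Nine of the 13 windows (56, 60, 64, 72, 76, 84, 88, 96, 100) have no scheduled sample.

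**4. Size of the split.** Assume visit days are spread evenly over the allowed range; the documents do not say so. With k days allowed either side there are 2k + 1 possible days. Of these, k + 1 (early or on time) take the lower label and k take the higher one.
- k = 1 (dosing footnote of Table 2-3): 2/3 and 1/3, or 67% and 33%.
- k = 2 (Section 9.1.2, QW): 3/5 and 2/5, or 60% and 40%.
- k = 3 (Section 9.1.2, Q2W): 4/7 and 3/7, or 57% and 43%.

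**5. Sensitivity to column position.** Shifting the whole lymphocyte row by one column either way, or by two columns to the left, still leaves 4 of 8 marks on a boundary. At 6-week spacing on even weeks, every second mark falls midway between SAP target weeks. A true spacing of 4, 8 or 12 weeks counted from week 52 would leave no mark on a boundary.

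**The case against.** **The 6-week schedule rests on table marks alone.** No prose states it, and some neighbouring marks are unreliable in the extracted text. Biweekly dosing in Table 2-2 appears in consecutive weekly columns, the pregnancy-test row of Table 2-3 is offset from the chemistry row, and the lymphocyte row of Table 2-4 shows no marks. Section 9.2.6 also lets sampling times change. This justifies checking the source table. It does not remove the point: the row spans the full width, is evenly spaced, ends at week 104 and matches the biomarker row. Other rows of the table fall on sensible weeks, a column shift changes nothing, and no 4-weekly pharmacodynamic schedule is documented.

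**Empty windows are not an error in themselves.** This stands. Appendix G must also place unscheduled, progressive-disease and end-of-treatment visits. The fault is that scheduled samples receive wrong labels.

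**The affected output is partly hidden.** This also stands. The SAP's pharmacodynamic section is largely redacted, and Protocol Section 10.4.2.4.2 speaks of selected time points. That by-visit tables will exist for the extension is inferred from SAP Section 9.1, whose default is to summarise all scheduled time points.

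**Stronger readings.** A reader might infer from the Schedule of Activities restriction in Appendix G that these samples are lost, because weeks 60, 64 and so on are not listed for lymphocyte subsets. The text does not support that. Week 62 is itself a scheduled lymphocyte visit, so it is applicable and kept. Nor does the problem cover everything after week 52, since the windows beyond week 108 are 2-weekly.

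**Conclusion.** The point holds for weeks 53 to 104. Four of the 8 scheduled lymphocyte-subset samples are labelled two weeks early or two weeks late, and a permitted one-day delay decides which. That count follows from the two tables and needs no assumption about visit timing. The 67/33, 60/40 and 57/43 splits do assume uniform timing and are only illustrative.

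The conclusion depends on the 6-week spacing being confirmed on the source table. The consequence is limited: no measured value changes, the summaries are descriptive, the SAP plans no statistical hypothesis for phase 1b, and the primary safety endpoints are unaffected. It is still worth correcting before the extension outputs are programmed, because the change is cheap and the groups are small.

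**What to change.** 1. Confirm the lymphocyte-subset spacing on the source version of Table 2-3. If it is 6-weekly, continue as below; if not, state the actual schedule and align the windows to it.
2. Replace the pharmacodynamic row for weeks 56 to 104 with n = 62, 68, ..., 98 at target -20/+21 days. The windows become 415-456, 457-498, 499-540, 541-582, 583-624, 625-666 and 667-708.
3. Give week 104 its own entry, days 709 to 743. At +21 it would run to 729 + 21 = 750 and overlap the week 108 window, which starts on day 744.
4. Keep week 52 at days 359 to 379. Extending it to day 414 would give that label to samples taken 414 - 365 = 49 days after its target. State instead how unscheduled, progressive-disease or early end-of-treatment samples on days 380 to 414 are assigned, for example to an unscheduled window left out of the by-visit summaries.

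All 8 scheduled samples then keep their own label at any offset within 3 days, against 4 of 8 now. The cost is a few SAP table entries and the matching program lines, with no change to data collection.

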#### Antibody assessments

Week 2, Day 15	15	2- 22
Week 4, Day 29	29	23- 43
Week n, Day $7^*n+1$ (n= 8, 12, 16,..., to 104 in increments of 4)	$7^*n+1$	Target day -13 days, Target day + 14 days
Week 108, Day 757	757	744, 764
Week n, Day $7^*n+1$ (n=110, ..., to 258 in increments of 2)	$7^*n+1$	Target day -6 days, Target day + 7 days
Week 260, Day 1821	1821	>1814
